**Ocular Exclusion Criteria:**

9. History of prior gene or stem cell therapy (ocular or other)
10. Pre-existing eye conditions that would preclude the planned treatment (i.e., injection) or interfere with the interpretation of study endpoints or surgical complications (examples include (but not limited to) glaucoma, diseases affecting the optic nerve causing significant visual field loss, active uveitis, corneal or lenticular opacities)
11. Cataract surgery, intraocular and/or peri-ocular injection in the study eye within six months prior to Day 0
12. Prior vitrectomy or aphakia in the study eye

**3.15.4 Early Discontinuation of Patients**

Patients may voluntarily withdraw from the study at any time or for the following reasons:

- a) Due to an adverse event (AE)
- b) If deemed necessary by the investigator or the sponsor that it is unsafe for the patient to continue in the study

When possible, the decision to withdraw a patient from study treatment or the study should be discussed with the sponsor. Notification of early patient discontinuation from the study and the

reason for discontinuation will be clearly documented on the appropriate Case Report Form (CRF).

In the case of a withdrawing patient, every reasonable attempt will be made to complete a final early termination visit (as shown in the study visit table). Patients who withdraw from the study prior to receiving the study treatment may be replaced.

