### **3.13 Provisions for Injury**

Any complications arising post injection will be managed in accordance with the investigator's standard of care.

It is not possible for RST-001 to be removed from the eye after injection.

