### 5.1.14 Long-term Follow-up Visits

Patients completing the Month 24 visit will participate in long-term follow-up visits. Patients will be asked to report any AEs that occur during this 3-year follow-up period. At Months 36, 48, and 60, patients will undergo the following study assessments conducted at yearly clinic visits:

- Concomitant medications and procedures
- AE review
- Visual acuity
- Complete ophthalmic examination

The procedures for these assessments will be the same as they were for the core study assessments.

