#### **Treatment of intraocular inflammation and immunogenicity**

In the event that immunogenicity is suspected by the investigator, topical, local, intraocular or systemic corticosteroid, corticosteroid-sparing and immunomodulatory therapy may be initiated, usually in an escalating fashion, in accordance with the investigator's practice, to control the inflammation. The patient will continue in the study and all additional assessments and visits will be documented in the source documents.

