10.0 EFFICACY ANALYSES

All analyses will be based on the observed data. *Baseline* for efficacy is defined as the last non-missing efficacy assessment before the first dose of study treatment. All confidence intervals will be 2-sided 95% confidence intervals, unless stated otherwise.

The efficacy parameter will be the change from baseline VA, full field sensitivity, ambulation, object detection discrimination, VEP, ERG, QoL (composite score of NEI VFQ-25 scores) for the study eye at the scheduled Post-treatment visits and will be summarized by visit and by treatment group separately for each phase.

The NEI-VFQ-25 consists of 25 vision-targeted questions that represent 11 vision-related quality of life subscales and one additional general health item. The 11 subscales are general vision (item 2), difficulty with near vision activities (items 5, 6, 7), difficulty with distance vision activities (items 8, 9, 14), limitations in social functioning due to vision (items 11, 13), role limitations due to vision (items 17, 18), dependency on others due to vision (items 20, 23, 24), mental health symptoms due to vision (items 3, 21, 22, 25), driving difficulties (items 15c, 16, 16a), limitations with peripheral vision (item 10), limitation with color vision (item 12), and ocular pain (items 4, 19). The general health item is item 1.

Responses to individual questions are recoded to scores using the following scoring system, with a higher score representing better functionality. For example, for question 1, a score of 100 is applied for a response of “1.” The summary score for each subscale is determined by taking the average across multiple items within each corresponding subscale. For subscales calculated based on multiple questions, at least one non-missing response is required (i.e., at least one question is answered). The overall composite score is then calculated by averaging over all 11 vision-targeted subscale scores, excluding the general health score. Items or subscales that are left blank are excluded from the calculation of average scores; e.g., if any of the 11 subscale scores is missing, the overall composite score will be calculated based on the mean of the non-missing subscales.

Table 10-1 VFQ-25 Coded Values for Each Item

Items	Response Level	Coded value
1, 3, 4, 15c ^a	1	100 (best)
	2	75
	3	50
	4	25
	5 ^b	0 (worst)
2	1	100 (best)
	2	80
	3	60
	4	40
	5	20
	6	0 (worst)
5-14, 16, 16a	1	100 (best)
	2	75
	3	50
	4	25
	5	0 (worst)
	6	Missing

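### Injected patients who leave early for safety reasons may be lost to scheduled eye follow-up, because the Month 36 to 60 visits are written only for Month 24 completers

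*Protocol*

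**What the plan says.** Treatment is a single intravitreal injection (Protocol synopsis; SAP 9.2). Protocol 3.13 states: "It is not possible for RST-001 to be removed from the eye after injection".

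Protocol 3.15.4 begins: "Patients may voluntarily withdraw from the study at any time or for the following reasons". Two reasons follow. One is an AE. The other is "If deemed necessary by the investigator or the sponsor that it is unsafe for the patient to continue in the study". The section adds that, when possible, "the decision to withdraw a patient from study treatment or the study should be discussed with the sponsor", and that for a withdrawing patient "every reasonable attempt will be made to complete a final early termination visit". Replacement is mentioned only for patients who leave before dosing.

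Protocol 5.1.14 sets entry to the later visits: "Patients completing the Month 24 visit will participate in long-term follow-up visits". The synopsis, 3.15.1.1, 3.15.1.2 and Section 5 likewise place long-term follow-up after Month 24 or after the two-year core visits.

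Three provisions work the other way:

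- Protocol 6.2.1, on suspected immunogenicity: "The patient will continue in the study and all additional assessments and visits will be documented in the source documents".
- Protocol 8.2 requires AEs still ongoing at exit to be followed up as appropriate, with no schedule.
- Protocol 8.3 makes SAEs reportable until at least 28 days after exit. It also requires every patient with an SAE to be followed, with the outcome reported.

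On analysis, SAP 10.0 says of efficacy: "All analyses will be based on the observed data". SAP 15.3 applies the same principle to the primary and secondary objectives, which brings in the visit-based safety measures.

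**The concern.** In a repeat-dose trial, withdrawal for an AE can at least stop exposure. Here it cannot: once the injection is given, the only thing withdrawal stops is data collection. The plan nevertheless makes a safety problem a permitted reason for leaving, and then bases entry to the last three years on having completed the first two.

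If patients leave for that reason, the follow-up is missing because of the outcome under study. Two kinds of result are exposed:

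- the visit-based Month 6 measures in SAP 11.2 (acuity, full field sensitivity, ambulation, IOP and imaging) and their later counterparts;
- the long-term safety picture to Month 60, which is the stated purpose of the extension.

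The study is first-in-human, with safety as its primary objective and Phase 1 groups of about three, so a single exit matters. The patient also loses scheduled eye examinations.

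**Working it through.** **The plan's only sample-size figure.** 3 × 3 in Phase 1 plus up to 12 in Phase 2a gives 9 + 12 = 21, as stated (9 + 6 = 15 at the low end). It was chosen empirically, and no dropout rate is given.

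**What an injected patient who leaves before Month 24 still has under the text**

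| Item | Covered after exit? | Source |
|---|---|---|
| The AE that prompted exit | Yes: recorded, counts toward the Grade 3 criterion, tabulated in the all-dosed Safety Population | SAP 5.0, 6.2, 11.1 |
| Other AEs ongoing at exit | Yes, as appropriate, no schedule | Protocol 8.2 |
| Course of an SAE | Yes, to outcome | Protocol 8.3 |
| New SAE | Only within a window of at least 28 days | Protocol 8.3 |
| New non-serious AE | No provision | none found |
| Eye examination | One best-effort termination visit | Protocol 3.15.4 |
| Month 36, 48 and 60 visits | No route in | Protocol 5.1.14 |

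**An exit at Month 1 (chosen example).** The scheduled visits still ahead are Months 3, 6, 9, 12, 18 and 24 (six core) and Months 36, 48 and 60 (three long-term), so 6 + 3 = 9 visits. One termination visit stands in their place. SAP 15.2 assigns visits to Month 6 only on Days 136 to 230. A termination visit soon after Month 1 falls outside that window, so the Month 6 measures are missing. In a group of three that is 1/3 = 33% of the group's Month 6 visit data.

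**Precision alone.** With zero late events seen in n patients, the exact one-sided 95% upper bound on the event rate is 1 − 0.05^(1/n).

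- n = 3: 1 − 0.05^(1/3) = 63.2%
- n = 2: 1 − 0.05^(1/2) = 77.6%

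This assumes that exit is unrelated to risk.

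**Informative exit (assumed inputs).** Let k of 21 leave for an AE. Let late-event risk be 30% to 50% in those who leave and 5% in those who stay. The rate over all injected patients is [k × p_leave + (21 − k) × 0.05] / 21.

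- k = 1: (0.30 + 1.00)/21 = 6.2% to (0.50 + 1.00)/21 = 7.1%
- k = 4: (1.20 + 0.85)/21 = 9.8% to (2.00 + 0.85)/21 = 13.6%

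Follow-up of those who stay shows 5% in each case. If risk is equal in leavers and stayers, there is no bias. These figures show direction and order of size under the stated assumptions. They are not estimates for this trial.

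**The case against.** The strongest reply is that 3.15.4 permits withdrawal and removes nobody, and that the protocol already protects the cases that matter most. Much of this stands, and it rules out several stronger readings.

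- A reader might infer that the patients with the worst course will drop out. The documents do not support this: withdrawal is optional and no exit rate is given.
- A reader might infer that only SAEs are followed, for 28 days. The 28 days is a minimum for reporting new SAEs. Follow-up of SAE patients to outcome has no time limit, and follow-up of ongoing AEs is mandatory, if loosely defined.
- A reader might infer that the main safety conclusion is biased. It rests on the absence of any related Grade 3 or greater AE. The event that causes an exit is already counted, SAP 11.1 displays AEs leading to discontinuation separately, and SAP 15.2 summarises the termination visit in an end-of-study row.
- A reader might cite the dog study, where ocular inflammation was stable or progressed in recovery (Protocol 3.6.2.1). That is largely the situation for which 6.2.1 keeps patients in the study, so it is weak support.
- A reader might call 3.15.4 and 6.2.1 flatly contradictory. They can be read as a general permission and a specific rule, but neither refers to the other. The 6.2.1 rule is tied to suspected immunogenicity and does not cover complications attributed to the injection itself (6.2.2).
- The mention of withdrawing from study treatment has a natural meaning between consent and Day 0, so it does not show that repeat-dose wording was carried over.

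None of this supplies scheduled eye examinations after the termination visit, captures new non-serious events, or opens Months 36 to 60 to an injected patient who left early.

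**Conclusion.** The point holds in a limited form. Injected patients who leave for an AE or a safety judgment may be lost to scheduled ocular follow-up. The following can be lost:

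- the visit-based Month 6 measures, if exit is earlier and no termination visit falls in the Month 6 window;
- all later scheduled eye examinations;
- new non-serious events after exit;
- new SAEs beyond the reporting window of at least 28 days.

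Because visit data are analysed as observed, the visit-based and long-term safety summaries may look more favourable than the experience of all injected patients. The case for the Grade 3 criterion being distorted by the AE that prompts exit is not made.

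The size cannot be computed from the documents. The one-third loss of Month 6 visit data assumes one exit at Month 1 in a group of three. The gap between 5% and 6.2% to 13.6% rests wholly on assumed exit numbers and risks. The change is still worth making, since safety observation missed after an irreversible first-in-human injection cannot be recovered later.

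**What to change.** 1. In Protocol 5.1.14, make long-term follow-up apply to all injected patients who have not withdrawn consent, in place of those completing Month 24. Make the matching change in the synopsis, 3.15.1.1, 3.15.1.2 and Section 5.
2. In 3.15.4, separate stopping core study procedures from ending data collection. Injected patients who stop core visits would be offered the existing safety assessments on the existing Table 2 and Table 3 timetable to Month 60: AE review, concomitant medications and, where they agree, visual acuity and the ophthalmic examination.
3. Reconcile 3.15.4 with 6.2.1 so that a site can tell how the two apply together. This need not set a clinical rule on withdrawal, and investigator and sponsor discretion can remain as written. A patient's right to withdraw consent is unaffected.

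The cost is protocol and consent wording, plus follow-up effort for a few patients. No new visit or procedure is needed.

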## **4 Treatments**

### **4.1 Identity of Investigational Product**

The treatment in this study has been called RST-001. RST-001 constitutes a non-replicating recombinant Adeno-Associated Virus serotype [REDACTED] vector containing a gene encoding the channelrhodopsin-2 protein (ChR2 ORF) formulated in [REDACTED] [REDACTED]. RST-001 is provided as a sterile frozen liquid.

### **4.2 Dosage and Administration**

The doses of RST-001 evaluated in this study will be:

- LOW dose = [REDACTED] vg/eye
- MID dose = [REDACTED] vg/eye
- HIGH dose = [REDACTED] vg/eye

### **4.3 Method of Assigning Patients to Dose Groups**

This is a sequential dose-escalation study. In Phase 1, three groups comprising of approximately but no less than three patients, will be enrolled one after the other, receiving first the low dose, then the mid, and finally the high dose.

Escalation is dependent upon the enrollment stopping rules and DSMC recommendation.

In Phase 2a, up to approximately 12 patients may then be enrolled in parallel at the maximum tolerated dose.

### **4.4 Dose Rationale**

The highest feasible concentration of RST-001 is constrained by manufacturing capabilities and product stability and has been determined to be approximately [REDACTED] vg/ml. The highest feasible dose is then limited by the volume that can be delivered to the human vitreous. Based upon estimated vitreous volumes and maximum feasible intravitreal dosing, this maximum

concentration was evaluated as the highest dose in our mouse pharmacology study (dose volume of 1  $\mu$ l) and mouse (1  $\mu$ l) and dog (█  $\mu$ l) toxicology and biodistribution studies. This dose was demonstrated to be efficacious and no dose-limiting toxicity was observed, respectively. Since the beagle dog vitreous has about half the vitreous volume of the human eye, the HIGH dose for the human study has been determined to be █ vg/eye given as a single 100  $\mu$ l intravitreal injection. In order to be safe and conservative but also balanced with the potential for delivering an active dose, Allergan proposes that the LOW initial starting dose for the first-in-human study be █ of this dose, █ vg/eye. The MID dose will be █ of the HIGH dose, █ vg/eye.

Dose escalation will proceed according to [Table 1](#), only after review by the DSMC (see [Figure 1](#), above). Three doses have been chosen with the safety as the priority but will provide a good opportunity to observe biological effect.

The rationale for the dosing schedule is once again based primarily on patient safety. Thus, at each dose a single patient will receive treatment followed by an intensive period of observation for any evidence of AEs prior to dosing the remaining two patients in the group. The safety and tolerability and optimal single dose of RST-001 will therefore be established in Phase 1. Phase 2a patients will receive a single intravitreal injection of RST-001 at the maximum dose tolerated by Phase 1 patients.

#### **4.5 Patient and Investigator Masking**

This is an open-label study so that patients and investigators will know which eye is treated and what dose of RST-001 was given.

#### **4.6 Packaging and Labeling**

Correct product identity, labeling and patient specificity will be assured by the use of standard operating procedures in accordance with FDA regulations. These operating procedures will include identifiers to ensure correct labeling to identify study treatment throughout manufacture, handling and administration.

#### **4.7 Handling and Storage**

The study treatment RST-001 is provided as a sterile frozen liquid and must be stored at █ °C or below. Stability testing indicates RST-001 is stable for at least █ °C or below. Please refer to the Study Procedures Manual for additional information.

## **4.8 Study Treatment Preparation and Administration**

RST-001 must be prepared under aseptic conditions as described in the Study Procedures Manual. Keep residual study treatment separately from unused study vials.

Immediately prior to study treatment administration, the patient will be placed in the supine position and the patient's eye will be prepared for injection in accordance with the description given in the Study Procedures Manual.

## **4.9 Product Accountability**

Study treatment will be shipped to the site after receipt of required documents in accordance with applicable regulatory requirements. RST-001 study treatment will be handled in accordance with regulatory and institutional requirements. RST-001 will only be administered to patients enrolled in the study who meet the eligibility criteria and who have signed the informed consent form. RST-001 will only be administered in accordance with the surgical procedure described in this document. Study treatment must be stored in a secure temperature-controlled area with access limited to the investigator and authorized study site personnel. The investigator or designated study site personnel is responsible for study treatment accountability, reconciliation and record maintenance. In accordance with all applicable regulatory requirements, the investigator or designated study site personnel must maintain study treatment accountability records throughout the course of the study. All study treatment must be returned to Allergan or Allergan designee at the completion of patient enrollment.

## **4.10 Assessment of Compliance**

Deviations with respect to dosage and administration will be documented by the investigator. Such deviations will be immediately reported to Allergan, the medical monitor, the institutional review board and the FDA, as appropriate.

## **4.11 Treatment of RST-001 Overdose**

There is no known treatment in the event of an overdose of RST-001.

## **4.12 Prior and Concomitant Therapy**

During the course of the study, patients will be allowed to continue taking prescribed and over-the-counter medications that are not excluded in the protocol (i.e., antiplatelets and anticoagulants prior to treatment, and immunosuppressive therapy).

## 5 Study Assessments and Intravitreal Injection

Patients diagnosed with advanced RP and who are eligible based on inclusion and exclusion criteria will be invited to participate in this study. After obtaining informed consent and authorization, patients will undergo a complete physical examination and laboratory testing to assess eligibility for the study.

Patients who meet inclusion criteria will be considered eligible for study entry and will receive a single intravitreal injection of RST-001. Following RST-001 administration (Day 0) patients will be assessed on the first post injection day (Day 1).

The visit schedule includes:

- Core study visits: Twelve visits are planned over 24 months, including Screening and Baseline visits, Day 0, Day 1, Day 7, and Months 1, 3, 6, 9, 12, 18, and 24.
- Long-term follow-up: After completion of the Month 24 visit, each patient will participate in a long-term follow-up study for a total of an additional 3 years. These visits include yearly office visits for 3 years (Months 36, 48, and 60).

Core study visits are described in [Table 2](#) and long-term follow-up visits are described in [Table 3](#).

Study visits may be impacted due to the COVID-19 pandemic. This may include changes such as telephone or virtual visits, visits at alternative locations, or changes in the visit frequency and timing of study procedures, among others. Additional details are provided in the subsequent section. Every effort is to be made to ensure the safety of subjects and site staff, while maintaining the integrity of the study. If visits cannot be conducted onsite due to travel restrictions or other pandemic-related reasons, follow the updates below on how to proceed.

During the COVID-19 pandemic, if it is not possible for all study procedures to be performed as specified due to travel restrictions or other reasons, the following modifications are allowed with agreement from the sponsor:

- If permitted by local regulations, the IRB/IEC, and the subject, postbaseline visits may be conducted virtually.
- Study Visits and/or activities are to be performed as scheduled whenever possible.

**Table 2** Study Visit Schedule: Core Study Visits

	Screening b	Baseline b	Day			Month					
			0	1	7 ± 1	1 ± 7	3 ± 7	6 ± 7	9 ± 7	12 ± 30	18 ± 30
Visit Windows (Days) a	-45 to -8	-7 to -1	0	1	7 ± 1	1 ± 7	3 ± 7	6 ± 7	9 ± 7	12 ± 30	18 ± 30
Informed Consent/Authorization	X										
Ophthalmic and Medical History	X	X	X								
Concomitant medications and procedures	X	X	X	X	X	X	X	X	X	X	X
Adverse Events review	X	X	X	X	X	X	X	X	X	X	X
Physical Examination	X										
Pregnancy Test	X	X									
Blood Sample d	X	X									
Electrocardiogram (ECG)	X										
Chest X-ray	X										
Visual acuity	X										
Full Field Sensitivity Testing (FFST)	X	X									
Object detection and discrimination	X	X									
Pupillometry (at selected sites)			X								
Ambulation			X								
Complete Ophthalmic Examination	X	X									
Intraocular Pressure (IOP)	X	X									
Spectral Domain Optical Coherence Tomography (SD-OCT)	X	X									
Color Fundus Photography and Autofluorescence			X								
Electroretinography (ERG)	X										
Visual Evoked Potentials (VEP)			X								
Quality-of-life questionnaire			X								
Study drug administration f											

a Assessment administration may extend over more than one day.b If convenient, the Screening and Baseline visits may be combined.c Month 24 or early termination visit.d Blood samples will include hematology, chemistry and RST-001 immunogenicity testing; see [Appendix 2](#) for details.e IOP measurements will be performed pre- and post-injection in the study eye only. After the intravitreal injection, the patient will remain in the supine position and (IOP) intraocular pressure will be monitored for at least 30 min. In the event that the IOP is 30 mmHg or above, this will be managed according to Section [5.3.2](#).f Topical corticosteroid treatment may be given to the injected eye according to the investigator's standard of care.

**Table 3** Study Visit Schedule: Long-term Follow-up Visits

	Months		
	Clinic Visits		
Visit Windows (Month $\pm$ Days)	36 $\pm$ 30	48 $\pm$ 30	60 $\pm$ 30
Concomitant medications and procedures	X	X	X
Adverse Events review	X	X	X
Visual Acuity	X	X	X
Complete Ophthalmic Examination	X	X	X

